5.4.1.4 Criteria for Assessing Causality

The Investigator is responsible for determining the relationship between the administration of SM and the occurrence of an AE as **not suspected** or as a **suspected** reaction to SM. These are defined as follows:

Not suspected: The temporal relationship of the AE to SM administration makes a **causal relationship unlikely**, or other drugs, therapeutic interventions, or underlying conditions provide a sufficient explanation for the observed event.

- **Not related:** Temporal relationship to SM administration is missing or implausible, or there is an evident other cause.

- **Unlikely related:** Temporal relationship to SM administration makes a causal relationship improbable; and other drugs, chemicals, or underlying disease provide plausible explanations.

Suspected: The temporal relationship of the AE to SM administration makes a causal relationship possible, and other drugs, therapeutic interventions, or underlying conditions do not provide a sufficient explanation for the observed event.

- **Possibly related:** Temporal relationship to SM administration is plausible, but concurrent disease or other drugs or chemicals could also explain event. Information on drug withdrawal may be lacking or unclear. This will be reported as a **Suspected Adverse Drug Reaction (SADR)**.
- **Definitely related:** Temporal relationship to SM administration is plausible, and concurrent disease or other drugs or chemicals cannot explain event. The response to withdrawal of the medication (dechallenge) should be clinically plausible. The event must be definitive pharmacologically or phenomenologically, using a satisfactory rechallenge procedure if necessary. This will be reported as an **Adverse Drug Reaction (ADR)**.

5.4.2 Serious Adverse Events (SAE)

AEs are classified as serious or non-serious. An AE or ADR is considered “serious” if, in the view of either the investigator or Sponsor, it results in one of the following outcomes:

- death
- life-threatening AE (i.e., the subject was at immediate risk of death from the AE as it occurred. This does not include an event that, had it occurred in a more severe form or was allowed to continue, might have caused death.)
- in-patient hospitalization or prolongation of existing hospitalization
- persistent or significant disability or incapacity or substantial disruption of the ability to conduct normal life functions
- a congenital anomaly or birth defect
- an important medical event

Important medical events are those that may not be immediately life threatening or result in death or hospitalization, but are clearly of major clinical significance. They may jeopardize the subject, and may require intervention to prevent one of the other serious outcomes noted above. For example, drug dependence or abuse, blood dyscrasias, a seizure that did not result in in-patient hospitalization, or intensive treatment for allergic bronchospasm in an emergency department would typically be considered serious.

5.4.2.1 *Investigator Responsibilities for Reporting SAEs*

The Investigator must immediately report to the Sponsor all SAEs, regardless of whether the Investigator believes they are drug related.

All SAEs must be reported to the Drug Safety Contact within 24 hours of first becoming aware of the SAE. The Investigator must complete an SAE eCRF in EDC and include a detailed description of the SAE,

as well as other available information pertinent to the case (e.g., hospital records, autopsy reports and other relevant documents). Should the site be unable to access EDC, a paper SAE form must be completed and sent to [REDACTED] Drug Safety by email or fax. The investigator will keep a copy of this SAE Report form on file at the study site. Once EDC becomes available, the site must complete the SAE eCRF in EDC.

The Investigator or study physician, after thorough consideration of all facts that are available, must include an assessment of causality of an AE to SM in the report to the Sponsor.

Follow-up information, or new information available after the initial report, should be actively sought and reported to the Sponsor as it becomes available using the SAE Report Form.

The Drug Safety Contact for SAE reporting is:

5.4.2.2 Other Events Requiring Immediate Reporting

The Investigator must report a pregnancy that occurs in a subject during a clinical study to the Drug Safety Contact within 24 hours of first becoming aware of the event. Pregnancy should be reported on a Pregnancy Report Form. The Investigator should discuss the case with the Medical Monitor; the Investigator must follow any pregnant subject for 3 months after the child is born. The Investigator must complete a Pregnancy Outcome Form as a follow up. Any AEs concerning the pregnancy of the subject during pregnancy or the child after birth must be documented and reported to the Sponsor.

Treatment-emerging EPS (e.g. akathisia, dystonia, Parkinsonism, tardive dyskinesia) and neuroleptic malignant syndrome should be reported to the Drug Safety Contact person(s) by completing the Adverse Event of Special Interest (AESI) eCRF in EDC. Should the site be unable to access EDC, a paper AESI form must be completed and sent to [REDACTED] Drug Safety by email or fax within 24 hours of first becoming aware of the event. Once EDC becomes available the site must complete AESI eCRF in EDC. EPS incidence will be summarized and shared with study Investigators throughout the trial.

Overdosage of molindone presumably may be manifested by severe EPS and sedation. Coma with respiratory depression and severe hypotension resulting in a shock-like syndrome could occur. In the event of a suspected overdose, the parent or legal representative should be instructed to call 911 or their local poison control center at [REDACTED].

Symptomatic, supportive therapy should be the rule. Gastric lavage is indicated for the reduction of absorption of molindone which is freely soluble in water. Since the adsorption of molindone by activated charcoal has not been determined, the use of this antidote must be considered of theoretical value.

Emesis in a comatose patient is contraindicated. Additionally, while the emetic effect of apomorphine is blocked by molindone in animals, this blocking effect has not been determined in humans.

5.4.2.3 Sponsor Responsibilities for Expedited Reporting of SAEs

The Sponsor will inform Investigators and regulatory authorities of reportable events, in compliance with applicable regulatory requirements, on an expedited basis (i.e., within specific timeframes). For this reason, it is imperative that study sites submit SAE information to the Sponsor in the manner described above.

Investigators must comply with the applicable regulatory requirements related to the reporting of SAEs to the IRB/IEC. Investigators must also submit the safety information provided by the Sponsor to the IRB/IEC unless the country legal regulation requires that the Sponsor should be responsible for the safety reporting to the IRB/IEC.

It is the responsibility of the Sponsor to notify all participating investigators, in a written IND safety report, of any SADR that is both serious and unexpected. The Sponsor will also notify participating investigators of any findings from other sources (other studies, animal and in vitro testing, etc.) that suggest a significant risk for human subjects. Such findings will typically lead to safety-related changes in the study protocol, Informed Consent, and/or Investigator's Brochure.

5.4.3 Management of Treatment-Emerging EPS

If a subject experiences treatment-emerging EPS (including akathisia, dystonia, Parkinsonism, or tardive dyskinesia), benztrapine will be permitted at a starting dose of 0.5 mg BID up to a range of 1 to 4 mg/day. Lorazepam (1 to 2 mg per dose not to exceed three times daily) and clonazepam (0.25 to 1 mg per dose not to exceed twice daily) will also be permitted to treat emerging EPS.

A positive finding on an EPS safety assessment scale (Barnes Akathisia, Simpson-Angus, AIMS) does not necessarily equate to an EPS event. Investigators should evaluate positive findings on the EPS safety assessment scales and integrate them into a global clinical observation to determine if an AE of EPS should be recorded.

5.4.4 Laboratory Measurements

With the exception of urine pregnancy test, clinical laboratory tests will be performed by a central laboratory as specified in the reference binder.

Details for collecting, handling, and shipping samples (including shipment addresses) will be detailed in a separate laboratory manual. The Schedule of Visits and Procedures ([Table 1](#)) shows the time points at which urine samples will be collected for urinalysis and blood samples will be collected for clinical laboratory tests and plasma concentration levels.

[Table 3](#) presents the clinical laboratory tests to be performed. Metabolic parameters (including insulin, glucose, triglycerides, and cholesterol) and prolactin will be measured. A subject will be excluded if the Screening blood test results indicates > 2 times the upper limit of normal (ULN) of alanine

aminotransferase (ALT), aspartate aminotransferase (AST), gamma glutamyl transpeptidase (GGT), and/or serum creatinine. Laboratory tests will not be repeated for these subjects.

All laboratory tests will be reviewed in a timely manner by qualified site personnel to ensure safety. Abnormal lab findings may be confirmed if necessary by one repeated testing at the discretion of the Investigator. Any repeat laboratory testing will be conducted under **fasting condition**. Any laboratory abnormality may qualify as an AE in the Investigator's judgment.

A total of approximately 42 mL of blood per subject will be drawn during the study: 22 mL is for clinical laboratory tests and 20 mL is for PK sampling.

Table 3: Clinical Laboratory Tests

Category	Parameters
Hematology	RBC, WBC, Hgb, HCT, MCH, MCHC, MCV, platelet count, and WBC with differential (neutrophils, lymphocytes, monocytes, eosinophils, basophils, large unstained cells)
Chemistry	Electrolytes: Na ⁺ , K ⁺ , chloride, bicarbonate
	Liver function tests: alkaline phosphatase, AST, ALT, total bilirubin, direct bilirubin, indirect bilirubin
	Renal function parameters: BUN, creatinine
	Other: glucose, Ca ⁺² , albumin, phosphorus, lactate dehydrogenase, total protein, CK/CPK, globulin, uric acid, triglycerides, insulin, prolactin, cholesterol – total, HDL and LDL Amylase, gammaGT (GGT), Iron, Lipase, Magnesium
Urine	Urinalysis Urine Drug Screen Urine pregnancy test (FOCBP only)

5.4.5 Vital Sign and Height/Weight Measurements

Vital sign measurements (e.g., blood pressure, heart rate, temperature, and respiratory rate) and height, weight and BMI will be obtained at visits designated on the Schedule of Visits and Procedures ([Table 1](#)). Blood pressure and heart rate will be measured after the subject has been sitting for 5 minutes. Vital signs may be taken at any other time, as deemed necessary by the Investigator.

5.4.6 Medical History

Medical history will be collected at visits designated on the Schedule of Visits and Procedures ([Table 1](#)).

5.4.7 Physical Examinations and Electrocardiograms (ECGs)

A physical examination and a 12-lead ECG will be obtained at visits designated on the Schedule of Visits and Procedures ([Table 1](#)). Additional ECGs may be performed at other times if deemed necessary by the Investigator.

The ECG will be recorded while the subject is resting in a supine position. The ECG will electronically measure the PR, QRS, QT, and QTc intervals, and heart rate.

All ECG tracings will be reviewed within 24 hours by the Investigator or qualified Sub-Investigator. PR intervals will be determined for each of these ECGs from a single reading. Invalid measurements will be repeated. QTc will be reported as QTcF (QT corrected using Fridericia's method).

5.4.8 Other Special Tests

The following special tests will be administered in the clinic at visits designated in the Schedule of Visits and Procedures ([Table 1](#)).

5.4.8.1 *K-SADS-PL 2013 Diagnostic Interview*

The K-SADS-PL 2013 is a semi-structured diagnostic interview designed to diagnose current and past episodes of psychopathology in children and adolescents according to DSM-5 criteria (Kaufman 1997). We will use a version of K-SADS 2013 that was revised to be compatible to the DSM-5 criteria. It includes the parent and child DSM-5 cross-cutting symptoms measures (DSM-5 CC-SM); an unstructured Introductory Interview; the Diagnostic Screening Interview; the Supplement Completion Checklist; the Diagnostic Supplements and the Summary Lifetime Diagnostic Checklist. The K-SADS-PL 2013 will be used at screening to confirm the diagnosis of ADHD, as well as to rule out exclusionary diagnoses. The Screen Interview will assess the different diagnoses and determine which supplements should be completed. Supplement 4 (Neurodevelopment, Disruptive and Conduct Disorders) must be completed to assess ADHD, ODD, CD Tic and ASD. If an exclusionary diagnosis is confirmed, the remainder of the diagnostic will not be completed. This assessment will be administered at Visit 1.

5.4.8.2 *Simpson-Angus Scale*

The Simpson-Angus scale is a 10-item rating scale that is widely used for assessment of neuroleptic-induced Parkinsonism (Simpson 1970). It consists of 1 item measuring gait, 6 items measuring rigidity, and three items measuring glabella tap, tremor and salivation, respectively. This assessment will be administered at Visit 3 and all subsequent visits.

5.4.8.3 *Barnes Akathisia Scale*

The Barnes Akathisia scale is a rating scale for drug-induced akathisia and includes components for rating the observable, restless movements characteristic of akathisia, the awareness of restlessness, and any distress associated with the condition (Barnes 1989). This assessment will be administered at Visit 3 and all subsequent visits.

5.4.8.4 *Abnormal Involuntary Movement Scale (AIMS)*

The AIMS test is a rating scale used to measure tardive dyskinesia (Munetz 1988). There are 12 items that rate involuntary movements of various areas of the subject's body. This assessment will be administered at Visit 3 and all subsequent visits.

5.4.8.5 Vitiello Aggression Scale

The Vitiello Aggression Scale is a 10-item rating scale that uses a cluster analysis to categorize aggression into two subtypes, predatory (or planned) and affective (or impulsive) (Vitiello 1990). This assessment will be administered at Visit 1.

5.4.8.6 Retrospective-Modified Overt Aggression Scale (R-MOAS)

The Retrospective-Modified Overt Aggression Scale (R-MOAS) was developed to gauge the severity of aggressive behavior (Blader 2010). Parents rate the frequency over the past week of 16 aggressive behaviors in four areas: verbal aggression; physical aggression toward others; aggression toward oneself; and destruction or hostile misuse of property. Numeric weighting amplifies the seriousness of more harmful behaviors in the total score. This assessment will be administered at Visit 1.

5.4.8.7 Columbia Suicide Severity Rating Scale (C-SSRS)

The C-SSRS is a questionnaire that prospectively assesses suicidal ideation and behavior using a semi-structured interview to probe patient responses (Posner 2011). The C-SSRS versions applicable to the current study are the Baseline version and the Since Last Visit version.

The Baseline version of the scale assesses lifetime suicidal ideation and behavior. This version is suitable as part of a subject's first interview and will be used at Visit 1 to identify volunteers who must not participate in the trial due to their suicidal tendencies.

The Since Last Visit version of the scale assesses any suicidal thoughts or behaviors the subjects may have had since the last administration of the C-SSRS. This version will be used for the other study visits.

5.4.8.8 Infrequent Behaviors Checklist

The infrequent behaviors checklist is a checklist of 15 behaviors that (along with the 15 IA Diary behaviors) were qualitatively linked to IA during the development of the IA diary. These behaviors include teasing, spitting, biting, weapons, ripping, breaking, vandalizing, destroying, fire setting, hitting animal, kicking self, kicking animal, severe injury self, severe injury others, severe injury animal. Caregivers will be asked which, if any, of these behaviors have been observed since the patient's last visit. This assessment will be administered at Visit 3, Visit 4, Visit 5, and Visit 6.

6 STATISTICAL METHODS

6.1 Statistical and Analytical Plans

Tabular summaries of the data collected during the study will be presented to provide a general description of the subjects studied and an overview of the Efficacy, PK and safety results. Data from all sites will be combined in the computation of these summaries and summaries will be presented by treatment group. Continuous variables will be summarized using descriptive statistics (number of subjects, mean, standard deviation [SD], median, and minimum and maximum values). Categorical (nominal) variables will be summarized using frequency tables (number and percentage of subjects in each category).

In addition to tabular summaries, subject data listings, as specified in Sections 16.2 and 16.4 of ICH Guidance E3, will be provided. Additional subject data listings to be provided for this study are listed under the relevant subsections below. All data analyses will be performed by the CRO after the study is completed and the database is released. Statistical programming and analyses will be performed using SAS® and/or other validated statistical software as required.

Complete details of the statistical analysis will be provided in a separate statistical analysis plan (SAP), which will be written, finalized, and approved prior to database lock and will be included in the Clinical Study Report (CSR) for this protocol. The statistical analysis plan will supersede the statistical analysis methods described in this clinical protocol. Any deviation from the statistical plan will be documented and described in the final report. If changes to principal features stated in the protocol are required, these will be documented in a protocol amendment. The final SAP will take into account any amendment to the protocol.

In general, the baseline value for a variable is defined as the last observation prior to the first dose of double-blind study medication, ideally Visit 3, but including the screening value, if necessary.

6.2 Handling Missing Data

For the primary efficacy end point, the frequency of IA behaviors during the treatment period will be calculated over the number of days with non-missing IA diary data in the treatment period. No explicit imputation of missing data will be used, but this approach is implicitly equivalent to using the frequency of IA behaviors during the days with non-missing IA diary data to impute the frequency for days after study discontinuation and days with missing IA diary data.

6.3 Analysis Populations

The population of “all enrolled subjects” consists of all those screened subjects who meet the requirements for study participation and are entered in the Baseline period of the study. The population of “all randomized subjects” consists of all those enrolled subjects who complete the Baseline Period, meet the inclusion/exclusion criteria and are randomized.

Safety Population: will include all randomized subjects who received at least 1 dose of study drug.

Intent-to-Treat (ITT) Population: will include all subjects who received at least 1 dose of study drug and have a baseline and at least 1 valid post-randomization assessment of frequency of IA behaviors based on IA diary entry.

Per-Protocol (PP) Population: will include all of the subjects in the ITT population who completed the treatment period with 80% diary completion compliance and who did not have major protocol deviations.

PK population: will include all subjects in the safety population who had at least one PK sample drawn which had a quantifiable concentration for at least one analyte of interest.

The safety, ITT, PP, and PK populations are based on randomized treatment received.

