6.6 Protocol Deviations

Protocol deviations will be presented in listings. If applicable, the number and percent of subjects within each type of protocol deviation will be presented using discrete summary statistics. Protocol deviations will include, but are not limited to:

- Non-compliance with any scheduled study visit
- Non-compliance with study treatment
- Disallowed concomitant medications
- Non-compliance with study inclusion or exclusion criteria
- Non-compliance with study assessment procedures

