7.3 Protocol Deviations

There are to be no Investigator-initiated deviations from the protocol. Any subject whose treatment deviates from the protocol or who is not qualified for study participation may be ineligible for analysis and may compromise the study. The date of and reason for deviations must be documented in all cases. Significant or major protocol deviations impacting the safety of the subject or the integrity of the study must be reported by the Investigator to the IRB immediately. Reporting of all other protocol deviations must adhere to the requirements of the governing IRB. Protocol assessments will continue until the end of the study, unless the protocol deviations put the subject at risk or the subject's condition requires that he/she be discontinued from the study.

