4 DEFINITIONS AND DERIVED DATASETS

Table 1. Terminology and Definition

| Terminology | Definition |
|-------------------------|---|
| Study Medication | SPN-810 or the matching placebo. |
| Study Day | The first dose date (Day 1) is defined as the date on which a subject took the first dose of double-blind study medication (SM), Other study days are defined relative to the Study Day 1. For visits prior to the first dose of the SM, Study Day is calculated as Visit Date – Day 1. For visits after the first dose, Study Day is calculated as Visit Date – Day 1 +1. |
| Enrolled | Subject has provided signed informed consent. |
| Randomized | Subject is assigned with the kit number for the SM. |
| Completer for the Study | Subject who completes the maintenance period (Visit 6). |
| Baseline | Unless specified otherwise, baseline is defined as the non-missing value collected most recent to and before the time of the very first dose of the SM. |
| Baseline Period | For subject daily IA diaries, on and prior to Visit 3 (inclusive, ≤Day 1). |
| Prior Medication | Medication collected on the Prior/Concomitant Medication CRF, with the start date prior to Study Day 1. |
| Concomitant Medication | Medication collected on the Prior/Concomitant Medication CRF, with end date on/after Study Day 1. |
| Titration Period | For subject daily IA diaries from Visit 3 through Visit 5 (v3< to ≤ V5) |
| Maintenance Period | For subject daily IA diaries from Visit 5 through Visit 6 (V5< to ≤ V6) |
| Treatment Period | Titration and Maintenance Periods combined |
| Derived Dataset | Derived dataset (analysis dataset) is any permanently stored collection of data containing raw and/or derived variables created to support the production of statistical summary tables. Derived variables will be created from the “raw” data. Analysis datasets to be created will include ADEFF (efficacy analysis dataset), ADSL (subject-level analysis dataset), ADAE (Adverse event analysis dataset) and other as appropriate. In deriving ADEFF, the source data include both the episodic diary and evening diary data files. Specifications for derived datasets will be developed which will include the names and definitions of derived variables in the derived SAS datasets. |

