7 STATISTICAL ANALYSIS

7.1 *Analysis Populations*

The population of “all enrolled subjects” consists of all those screened subjects who meet the requirements for study participation and are entered in the Baseline period (i.e., distributed IA diary) of the study. The population of “all randomized subjects” consists of all those enrolled subjects who complete the Baseline Period, meet the inclusion/exclusion criteria and are randomized.

7.1.1 *Safety Population*

The safety population will include all randomized subjects who received at least 1 dose of study drug and have at least one post-randomization safety measurements.

7.1.2 *Intent-to-treat (ITT) Population*

The intent-to-treat population will include all subjects who received at least 1 dose of study drug and have a baseline and at least 1 valid post-randomization assessment of frequency of IA behaviors based on IA diary entry. Subjects will be analyzed according to the treatment to which they were randomized.

7.1.3 *Per Protocol (PP) Population*

The per protocol population will include all of the subjects in the ITT population who completed the treatment period (Completed Maintenance Visit 6) with 70% diary completion compliance and who did not have major protocol deviations. Diary compliance is calculated as

$$\text{diary compliance} = \frac{\text{number of days diary completed within the treatment period}}{\text{Number of treatment days}} \times 100\%$$

Detailed specification of the PP population will be provided prior to the database lock for the final analysis.

7.2 *Disposition of Subjects*

Subject disposition and reasons for screening failure will be summarized for screen-failed subjects (Table 14.1.1).

Subject randomization schedule will be listed. Subjects whose randomization codes are unblinded during the conduct of the study will be listed along with the reason for un-blinding (Listing 16.1.7).

The following summaries and listings will be based on all randomized subjects.

Subjects (n and %) who completed and discontinued from the study will be tabulated by the treatment group for (1) Randomized, (2) ITT, (3) Safety, and (4) PP populations (Table 14.1.2a – Table 14.1.2d). The primary reasons for study discontinuation will be included in the tabulation. The primary reasons may include any of the following:

- Subject withdrew consent
- Lost to follow-up
- Administrative reason
- Adverse event
- Investigator decision
- Failure to follow required study procedures
- Other

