In addition, subject disposition will be summarized by treatment period (combined titration and maintenance, titration, maintenance, and tapering) for (1) Randomized, (2) ITT, (3) Safety, and (4) PP populations (Table 14.1.3a – Table 14.1.3d).

In addition, subject's enrollment will be summarized by study site among ITT population (Table 14.1.4).

A data listing will be presented for subjects who do not complete the treatment along with the reasons for discontinuation (Listing 16.2.1.1).

7.3 *Protocol Deviations*

Protocol deviations will include, but are not limited to

- Non-compliance with any scheduled study visit
- Non-compliance with study treatment
- Prohibited medications
- Non-compliance with study inclusion or exclusion criteria
- Non-compliance with study assessment procedures

Subjects with major protocol deviations will be listed based on all randomized subjects. The listing will include a brief description of the deviation, deviation category, and if applicable, study day when deviation occurred along with other pertinent information (Listing 16.2.1.2).

If warranted, subjects (n and %) with major protocol deviations will be tabulated by treatment group and deviation category (Table 14.1.5a).

Additionally, subjects (n and %) in each analysis population with major protocol violations will be tabulated by treatment group (Table 14.1.5b). Subject's inclusion/exclusion from each analysis population will be listed along with the applicable reasons for exclusion (Listing 16.2.1.3).

Summary (n and %) of the analysis population will also be presented by treatment groups for the randomized population (Table 14.1.6).

7.4 *Demographics and Baseline Subject Characteristics*

Subject age, sex, ethnicity, race, height at screening, weight at screening and baseline will be summarized based on the ITT, Safety and PP populations by treatment group. Age will be summarized as a continuous variable as well as a categorical variable (6 to 9 [i.e., <10], and 10 to 12 [i.e., ≥10 and ≤ 12] years, inclusive) (Table 14.1.7a – Table 14.1.7c).

All demographic and baseline characteristics will be included in the subject data listing (Listing 16.2.1.4).

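### The definition of all randomized subjects requires eligibility, so read literally a dosed but ineligible child is outside Safety and the major-deviation listing while remaining in ITT

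*Protocol*

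**What the plan says.** Protocol 6.3 defines the population of all randomized subjects as "all those enrolled subjects who complete the Baseline Period, meet the inclusion/exclusion criteria and are randomized". SAP 7.1 uses the same terms: "enrolled subjects who complete the Baseline Period, meet the inclusion/exclusion criteria and are randomized".

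The Safety population rests on that set. Protocol 6.3 says it "will include all randomized subjects who received at least 1 dose of study drug". SAP 7.1.1 begins the same way, "The safety population will include all randomized subjects who received at least 1 dose of study drug", and adds the need for a post-randomisation safety measurement. SAP 7.8 runs every safety summary on this population.

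SAP 4 has a separate entry for the term Randomized: "Subject is assigned with the kit number for the SM". It has no eligibility condition.

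On deviations, protocol 6.6 names "Non-compliance with study inclusion or exclusion criteria" as a category, and SAP 7.3 carries the same category. SAP 7.3 then states: "Subjects with major protocol deviations will be listed based on all randomized subjects". Appendix 2 of the SAP assigns that listing (16.2.1.2) to the Randomized Population.

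Protocol 7.3 adds: "Any subject whose treatment deviates from the protocol or who is not qualified for study participation may be ineligible for analysis".

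**The concern.** A Safety population is meant to hold everyone who was exposed to study drug. A deviation listing is meant to show, among other things, who was randomised without qualifying. If eligibility is part of what makes a subject randomized, both outputs leave out the subjects for whom the question arises.

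At stake are the completeness of the by-arm safety tables and openness about eligibility breaches. There is also an odd asymmetry: the same child could count towards efficacy and not towards safety, and neither document gives a reason for that. Because SAP 4 and SAP 7.1 point different ways, two programmers could build different Safety populations from the same SAP.

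**Working it through.** The plan states no figure here, so the check is one of set membership. Take one child who was assigned a kit, took at least one dose, has a baseline and post-randomisation diary data, has a post-randomisation safety measurement, and is found not to have met a criterion. Suppose the breach is classed as a major deviation.

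| Set or output | Source | Literal SAP 7.1 definition | SAP 4 definition alone |
|---|---|---|---|
| All randomized subjects | Protocol 6.3, SAP 7.1 | Out | In |
| Safety population and summaries | Protocol 6.3, SAP 7.1.1, SAP 7.8 | Out | In |
| Listing 16.2.1.2, major deviations | SAP 7.3, Appendix 2 | Out | In |
| Listing 16.2.1.3, reasons for exclusion from populations | SAP 7.3, Appendix 2 | Out | In |
| Listing 16.2.3.1.1, all adverse events (on Safety) | Appendix 2 | Out | In |
| Listings 16.2.3.1.2 to 16.2.3.1.5, serious events, deaths, discontinuations, special interest | Appendix 2 | Out | In |
| ITT population | Protocol 6.3, SAP 7.1.2 | In | In |
| Table 14.1.5a, major deviations (on ITT, if warranted) | SAP 7.3, Appendix 2 | In | In |
| Per-Protocol population | SAP 7.1.3 | Out | Out |

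Three steps lie behind the table.

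1. SAP 7.1 sets three joint conditions: Baseline completed, criteria met, randomized. Using SAP 4 to interpret the third condition leaves the second in force. Kit assignment is then necessary but not sufficient, so SAP 4 competes with SAP 7.1 and does not settle it.
2. ITT starts from all subjects who were dosed and have the required diary data. It does not refer to the randomized set, so the eligibility condition does not reach it. This is why the child is in ITT and not in Safety.
3. The deviation category is not empty everywhere. Protocol 6.6 names no population for its listings, and Table 14.1.5a is on ITT. The gap is in the outputs built on the Randomized Population, chiefly Listing 16.2.1.2.

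On size, the documents give no rate of late-found ineligibility. Purely as an illustration, assume 1% to 5% of those randomised:

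- Protocol total of 330: 0.01 × 330 = 3.3 and 0.05 × 330 = 16.5, so about 3 to 17 children.
- SAP 3.5 total of 3 × 153 = 459: 0.01 × 459 = 4.6 and 0.05 × 459 = 23.0, so about 5 to 23 children.

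These counts assume that every such child was dosed. The true number could be zero.

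**The case against.** The strongest reply is that the clause describes the gate at randomisation and is not a later filter. Protocol 3.2.2.1 has the criteria re-assessed before randomisation. Protocol 4.3.4 and SAP 3.3.3 describe the same sequence: finish Baseline, still qualify, receive a kit number. Nothing says that a subject leaves the randomized set when a breach comes to light. Protocol 6.5 describes the Safety set simply as subjects treated. Listing eligibility breaches among all randomized subjects makes sense only if that set can contain ineligible ones. This reading is plausible, and it is probably what was meant. It makes the loss uncertain, but it does not remove the condition from the text or reconcile SAP 7.1 with SAP 4.

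Several stronger readings are tempting, and the documents do not support them.

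- *The randomised comparison is broken.* It is not. ITT has no eligibility condition, and SAP 7.1.2 analyses subjects by randomised arm.
- *Protocol 7.3 licenses removal from ITT.* It is a general caution in the documentation section. SAP 1 says the SAP supersedes the protocol's statistical methods, and in the SAP only the Per-Protocol population drops major deviations.
- *Late-found ineligibility is to be expected because Visit 3 samples go to a central laboratory.* The explicit drug-test exclusion (protocol 4.1.2) and the liver and creatinine exclusion (protocol 5.4.4) are tied to Screening. The urine pregnancy test is not a central-laboratory test and must be negative for the subject to continue. Only a narrow route remains, through the undated requirement for normal laboratory profiles or a drug screen bearing on recent substance use.
- *Serious events would go unreported.* The reporting duties in protocol 5.4.2 do not depend on analysis populations. The issue is which planned tables and listings show the events.

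**Conclusion.** The point holds as a defect of definition. As written, protocol 6.3 and SAP 7.1 leave a randomised, dosed but ineligible child out of Safety. Through SAP 7.3 and Appendix 2, the child is also out of the major-deviation listing and the key adverse-event listings. This contradicts SAP 4 and sits badly with SAP 7.3's own deviation category.

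The consequence is limited to safety reporting and to transparency about eligibility breaches. The primary efficacy analysis and the sample size are untouched. Whether any child would be lost depends on how the clause is read when the datasets are built and on how many breaches are found after randomisation. The documents settle neither, and the 1% to 5% range is an assumption. The change is worth making because the conflict is real and the correction costs almost nothing.

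**What to change.** In protocol 6.3 and SAP 7.1, delete the condition on meeting the inclusion/exclusion criteria and define the set by assignment alone, for example: *all randomized subjects are all subjects assigned a kit number through the IWRS, whether or not they are later found ineligible.* This matches SAP 4, and the Randomized Population in Appendix 2 then takes the same meaning.

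The child in the check would then enter the Safety population (given the safety measurement that SAP 7.1.1 requires), Listings 16.2.1.2 and 16.2.1.3, and the adverse-event listings. Per-Protocol could still exclude the child for a major deviation.

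For consistency, state in protocol 7.3 that deviations or ineligibility may lead to exclusion from the Per-Protocol population only.

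The cost is wording in three places, with no new data, patients or analyses.
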